6.2.6 Assessment of statistical assumptions

Statistical assumptions will be assessed using appropriate tools and diagnostic plots. Alternative models have been described above.

6.3 Interim analyses

No interim analyses are planned.

6.4 Missing data

For missing data on outcomes and covariates, we use multiple imputation by chained equations (MICE), under the assumption of missing at random (MAR). Ten imputation datasets will be created

SAP for PHYTOBRONCH	Version of SAP: 1	
Based on template: CTU_STA_TEM-11; v5.0.0	Valid from: 20.03.2025	Page 14 of 15

and results pooled using Rubin's rule. The following auxiliary variables will be used to predict missingness: type of recruitment (PCP/walk-in clinic), age, sex, level of education, smoking status, beginning of symptoms (number of days), and baseline ABSS. Variables with missing values will be removed from the auxiliary list of variables. Terminal events such as death will be used as auxiliary variables. Technical issues (e.g., wrong email, reminder not sent) that cause missingness will also be used as auxiliary variables. For the PP analyses, we will also use inverse probability of attrition weights, which will be combined to inverse probability weights accounting for ICEs by a multiplication. We will use stabilized weights, truncated at the 99th percentile.

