2.3 Sample size

The sample size was calculated for each of the co-primary outcomes, using a Bonferroni correction for the significance level (.05 / 2 = .025). It was replicated in Stata 18 as follows:

- Reduction of symptom severity: Using a two-sample means test with power = 80%, a two-sided significance level = 2.5%, an allocation ratio 1:1, one day of difference between groups (Δ=1), and a standard deviation of 3 days assumed to be the same in both groups (1), we needed n=346 (173 in each group).
- Antibiotics use: Using a two-sample proportions test (Pearson's chi-squared test) with power = 80%, a two-sided significance level = 2.5%, an allocation ratio 1:1, a proportion of 60% in the control group and 45% in the intervention group (Δ =15) (2), we needed n=420 (210 in each group).

The largest sample size estimation was selected: n=420. As this approach is rather conservative (e.g., it does not consider the fact that the co-primary outcomes may be correlated), we did not account for potential drop-out in the sample size calculation.

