Handling of intercurrent events: All participants are included. Participants who took antibiotics at baseline will be considered as failures (having antibiotics).

Handling of missing data: Missing data will be multiple imputed (see section 6.4).

* Same adjustment as E1.1. If there are too few participants, we will use analyses adjusting separately for each covariate + type of recruitment.

Estimand E2.2: This estimand quantifies the efficacy of the treatment assessed with the proportion of antibiotics use (co-primary outcome) in the PP population.

Outcome of interest: same as estimand 2.1.

Population-level summary measure of outcome: same as estimand 2.1.

Participant-set of interest: PP.

Handling of intercurrent events: Participants with ICE1-3 are excluded from the analysis. The data will be weighted according to inverse probability weighting for ICE 1 and 2 (see section 6.2.2).

Handling of missing data: As ICE cannot be assessed in participants who drop out or are lost to follow-up, we will not use multiple imputation. We will use inverse probability of attrition weights to account for attrition and multiple imputation for missing baseline covariates (see section 6.4).

Estimand E3.1: This estimand quantifies the incidence of AEs and SAEs.

Outcome of interest: Presence of any adverse or severe adverse event (binary) during the follow-up (up to 22 days).

Population-level summary measure of outcome: adjusted^{*} hazard ratio.

Participant-set of interest: SAF.

Handling of intercurrent events: All participants are included.

Handling of missing data: No missing data, participants are censored when the study ends (at day 22) or at the day of last contact.

* 1) Adjusted for the type of recruitment (PCP/walk-in clinic) and 2) adjusted for the following factors at baseline: type of recruitment, age, sex, level of education, smoking status, beginning of symptoms (number of days), and baseline ABSS. If there are too few participants, we will use analyses adjusting separately for each covariate + type of recruitment.

Estimand E3.2: This estimand quantifies the incidence of AEs and SAEs.

Outcome of interest: same as estimand 3.1.

Population-level summary measure of outcome: same as estimand 3.1.

Participant-set of interest: SAF without ICE2.

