6.1 Outcome definitions

Reduction of symptom severity. The first co-primary endpoint uses the patient-reported outcome Acute Bronchitis Severity Score (ABSS), which quantifies the severity of 5 symptoms related to acute bronchitis for the previous 24 hours. It is assessed on a scale from 0 to 4, with the sum score ranging between 0 and 20 (see Table 1) (3). Participants will complete the ABSS daily on an online diary, until symptom resolution and up to 21 days. If the participant does not answer, the ABSS will be evaluated in phone interviews (days 4, 8, and 22).

Symptom	0	1	2	3	4
Overall severity of illness	Very mild	Mild	Moderate	Serious	Very serious
Day cough	1-2 times/day	3-5 times/day	6-10 times/day	11-20 times/day	>20 times/day
Night cough	1-2 times/night	3-5 times/night	6-10 times/night	11-20 times/night	>20 times/night
Limit daily activity	None	Mild	Moderate	Severe	Very severe
Subjective fever	None	Mild	Moderate	Severe	Very severe

Table 1. Acute Bronchitis Severity Score (ABSS)

The first co-primary is the number of days needed to achieve a 50% reduction in the ABSS after peak of symptoms (1). The peak of symptoms is defined as the highest ABSS observed during the study.

The procedure to calculate the first co-primary endpoint is the following:

- Calculate daily ABSS (sum score of the 5 symptoms)
- Calculate the peak (max. ABSS observed)
- Calculate daily percentage change in the ABSS after the peak
- Calculate which day corresponds to a 50% decrease
- Calculate the number of days between the peak and the 50% decrease

If there is no peak, the first day will be used as the peak. If the 50% decrease is not reached, we will set the number of days to the maximum (22 days). Imputation will be used for missing values on daily ABSS (see section 6.4). We will run a sensitivity analysis computing the primary outcome and using multiple imputation on the primary outcome.

Antibiotics use. The second co-primary endpoint is the proportion of participants who take antibiotics after the initial visit (\geq day 2). It is defined as 0=no antibiotics during the same illness episode and 1=antibiotics use during the same illness period. Antibiotics use is assessed daily in the diary (day 1 to 21) until symptom resolution and at the three phone calls at day 4, 8, and 22.

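### Antibiotic use (co-primary 2): on the plain reading of 6.4, imputation ignores observed antibiotic-free time, so the risk ratio can be biased when loss differs by arm; direction and size are open

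*Combined protocol and SAP*

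**What the plan says.** - **Endpoint.** Section 4.3 (E2.1) makes antibiotic use after the initial visit a binary outcome, summarised by an adjusted risk ratio in the full analysis set. Section 6.1 codes it 1 for any use and 0 for none within the same illness episode.
- **Data collection.** Section 6.1: "Antibiotics use is assessed daily in the diary (day 1 to 21) until symptom resolution and at the three phone calls" (days 4, 8 and 22). Partial follow-up is therefore recorded, and the diary stops by design once symptoms resolve (also section 2.7).
- **Missing data.** E2.1: "Missing data will be multiple imputed (see section 6.4". Section 6.4: "For missing data on outcomes and covariates, we use multiple imputation by chained equations (MICE), under the assumption of missing at random (MAR". It lists type of recruitment, age, sex, education, smoking, days since onset and baseline ABSS, and adds terminal events and technical issues. It does not list day of last contact, antibiotic-free days, ABSS after baseline or randomised group.
- **Other endpoints.** Section 6.1 imputes the ABSS at the daily level and keeps imputation of the derived outcome as a sensitivity analysis. Section 6.2.2 right-censors drop-outs for adverse events. Section 6.2.5 has a Cox model for time to antibiotics, but only as an additional analysis.

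No section states the level at which antibiotic use is imputed. None states how to code a participant who is lost antibiotic-free, or one who resolves antibiotic-free and misses the day-22 call.

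**The concern.** A single recorded start settles the endpoint at 1, whatever happens later. A value of 0 needs the whole episode. Among participants who are lost, those who had started are therefore known, and only those who had not can be missing. If the whole-episode value is then imputed from the section 6.4 list, a participant seen antibiotic-free to day 8 is given roughly the risk of a participant followed from the start. The risk that actually remains after day 8 is not used. Given those predictors, missingness depends on the outcome, which is what MAR rules out. Adding randomised group to the imputation model would not cure this.

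The result at stake is the RR for a co-primary endpoint tested at 2.5%. The trial is open-label and only one arm receives a study product, so unequal loss is plausible. Section 2.3 makes no allowance for drop-out.

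**Working it through.** **1. The plan's own figure.** Inputs from section 2.3: "a proportion of 60% in the control group and 45% in the intervention group"; "a two-sided significance level = 2.5" (per cent); "an allocation ratio 1:1"; "Using a two-sample proportions test (Pearson's chi-squared test) with power = 80" (per cent).

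n per arm = [z(0.9875)·√(2·p̄(1−p̄)) + z(0.80)·√(p1(1−p1) + p2(1−p2))]² / (p1−p2)², with p̄ = 0.525

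= [2.2414 × 0.7062 + 0.8416 × 0.6982]² / 0.15² = 209.4, rounded up to 210. This agrees with the plan: "we needed n=420 (210 in each group". The planning RR is 0.45/0.60 = 0.75.

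**2. Expected rate when the whole-episode value is imputed within arm.** Four quantities are needed. Only p has a planning value in the documents.

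- p: true whole-episode risk (60% and 45% are planning values; 30% is an assumed lower rate)
- d: share lost (assumed 5% to 15%)
- e: share of starts among lost participants that are seen before loss (assumed 0.5 or 0.8)
- r: share of antibiotic-free losses already resolved, coded 0 and with no later use (assumed 0, 0.5 or 0.7, equal in both arms)

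Expected rate = [(1−d)p + d·p·e] / [(1−d) + d·p·e + d·r·(1−p·e)]

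The numerator is the known 1s. The denominator is all known values.

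**3. Worked case: p = 0.60 in both arms, e = 0.8.**

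- r = 0, control d = 0.15: (0.510 + 0.072)/(0.850 + 0.072) = 0.582/0.922 = 63.1%.
- r = 0, Kaloba d = 0.05: (0.570 + 0.024)/(0.950 + 0.024) = 0.594/0.974 = 61.0%. RR = 0.97.
- r = 0.5: the denominators gain 0.15 × 0.5 × 0.52 = 0.039 and 0.05 × 0.5 × 0.52 = 0.013. The rates are 0.582/0.961 = 60.6% and 0.594/0.987 = 60.2%. RR = 0.99.

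**4. RR under no true effect, loss 15% control and 5% Kaloba.**

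| p | e | r = 0 | r = 0.5 | r = 0.7 |
|---|---|---|---|---|
| 30% | 0.8 | 0.94 | 0.98 | 1.00 |
| 30% | 0.5 | 0.96 | 1.01 | 1.03 |
| 60% | 0.8 | 0.97 | 0.99 | 1.00 |
| 60% | 0.5 | 0.98 | 1.02 | 1.03 |

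**5. Where the bias changes sign.** The remaining risk of a participant lost antibiotic-free and unresolved is p(1−e)/[(1−p·e)(1−r)]. For p = 0.60 and e = 0.8 this is 0.12/0.52 = 23% at r = 0 and 46% at r = 0.5. The bias is zero when this equals p, that is when r = e(1−p)/(1−p·e). With e = 0.8, that is r = 0.74 (p = 30%) or 0.62 (p = 60%). With e = 0.5 it is 0.41 or 0.29. Above that value the bias reverses.

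**6. At the planning rates (60% vs 45%, true RR 0.75).**

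| Loss, control / Kaloba | e | r = 0 | r = 0.5 |
|---|---|---|---|
| 15% / 5% | 0.8 | 0.729 | 0.748 |
| 5% / 15% | 0.8 | 0.792 | 0.762 |
| 10% / 10% | 0.8 | 0.760 | 0.755 |
| 15% / 5% | 0.5 | 0.736 | 0.764 |
| 5% / 15% | 0.5 | 0.777 | 0.742 |
| 10% / 10% | 0.5 | 0.756 | 0.753 |

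Equal loss moves the RR little.

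**7. Does using the partial history help?** A simulation used 210 per arm, 10 imputations within arm and 1,500 replicates, with early starts predominating. Drop-out was unrelated to outcome, and no one was coded 0 on resolution (r = 0). Loss was 20% in one arm and 5% in the other.

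- Both true rates 60%: whole-value imputation rejected in 5.4% to 5.6% of replicates, imputation of the remaining days in 2.6% to 3.0%, and full data in 2.7%.
- True rates 60% vs 45%: whole-value RRs were 0.717 (control loses more) and 0.806 (Kaloba loses more). Remaining-day imputation gave 0.751 and 0.744, the same as full data.

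These rejection rates apply to r = 0 and a harsh loss pattern. They do not predict this trial's error rate.

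**The case against.** The other side has four arguments.

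- **The SAP does not say that the single value is imputed.** It is silent on the level. Auxiliary variables are usually additional to the analysis variables, and section 6.1 sends daily ABSS to section 6.4, so symptom course may enter the chained equations. This stands as a limit on what can be asserted. It does not rescue the text, because nothing in it brings in antibiotic-free time.
- **Resolution supplies known 0s.** The diary ends at resolution and 0 refers to the illness episode, so a participant who resolves antibiotic-free can naturally be read as 0 even if the day-22 call fails. These known 0s offset the known 1s. The participants still missing are symptomatic, with a higher remaining risk. This stands, and by the table in step 4 it can cancel or reverse the bias.
- **The day-22 call recovers the endpoint for anyone reached.** This also stands. Only participants not reached matter.
- **Loss rates and timing of starts are assumed.** This is correct, and so is the further point that drop-out driven by worsening symptoms would change the bias again.

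A reader might infer that the plan inflates antibiotic use in the arm that loses more patients, and so favours Kaloba if control loses more. The documents do not support this. It requires r near zero, and they give neither r, nor loss by arm, nor the timing of starts.

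**Conclusion.** The point holds in a limited form. On the plain reading of sections 4.3, 6.1 and 6.4, the imputation model for antibiotic use leaves out recorded information that determines who can be missing. MAR therefore does not hold given the listed predictors. The RR for co-primary 2 under E2.1 can be biased, mainly when loss differs by arm.

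Neither direction nor size is established. With no true effect and 15% vs 5% loss, the RR is about 0.94 to 0.98 if no resolved participant is a known 0. It is about 0.98 to 1.03 if 50% to 70% of antibiotic-free losses had resolved and count as 0. Both ranges assume imputation within arm, r equal in both arms, and drop-out otherwise unrelated to later antibiotic need.

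This is more than a request for detail: a better method is available from data already collected, and the current text leaves the choice open until after the data are seen. It affects a co-primary endpoint and should be settled before database lock. It does not show that the planned result will be wrong. E2.2 is outside this point, because that estimand does not impute the outcome.

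**What to change.** In section 6.4, with a cross-reference from E2.1:

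1. State that participants who resolved without antibiotics are coded 0, or are followed to day 22 for this endpoint.
2. For the others, impute antibiotic use by contact interval (days 2–4, 5–8, 9–22) from the last observed contact. Do this only among those antibiotic-free so far, conditional on randomised group, baseline covariates and ABSS to date. Then form the binary endpoint.
3. Keep imputation of the whole-episode value as a sensitivity analysis, as section 6.1 does for the ABSS.

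A day-22 risk per arm estimated with censoring at last contact is an alternative only if resolved participants are not censored at resolution. Otherwise it discards their known antibiotic-free outcome and overstates use. It also leaves out ABSS to date unless that is added.

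The cost is SAP wording and slightly more programming. The diary and calls already supply the data, and the time-to-antibiotics analysis in section 6.2.5 needs the same dates. Interval imputation still assumes that loss is explained by the recorded history; it does not protect against loss driven by unrecorded worsening.

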4.1 Confidence intervals and *P* values

Statistical tests will be two-sided with a 5% significance level, except for the co-primary outcomes, for which a 2.5% significance level is used. We will present 95% confidence intervals, used to assess the precision of the estimates. We will not calculate p-values for baseline comparisons.

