6.2 Analysis methods

6.2.1 Primary analysis

The primary analysis will be done according to the FAS (ITT) and PP sets specified in section 4.2, using the adjusted model (4, 5). The randomization group will be used as the main predictor, adjusting for the stratification factors and relevant predefined covariates. To account for the fact that participants are clustered in PCP practices, we will use bootstrapped standard errors (1000 reps). A random seed will be predefined for replicability. The intraclass coefficient is expected to be small. All effects will be shown using marginal point estimates (accounting for adjustment variables) and 95% confidence intervals.

For the first co-primary endpoint, reduction in ABSS, we will use a linear regression, e.g.:

bootstrap, reps(1000) seed(XXX): regress y x1 x2

This endpoint should be normally distributed, as observed in previous studies (3). However, if it is not normally distributed, we will use a log-transformation after adding the constant 1.

For the second co-primary endpoint, *proportion of antibiotics use*, we will use a logistic regression, e.g.:

bootstrap, reps(1000) seed(xxx): glm y x1 x2, fam(bin) link(log) eform

We will use multiple imputation to handle missing values on covariates and outcomes (see section 6.4). If there is collinearity between covariates, we will remove one collinear variable based on theoretical reasons.

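### Ten imputations and no stated imputation seed make each co-primary verdict depend more on random draws than it needs to; 100 imputations would largely cure this at the cost of computing time

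*Combined protocol and SAP*

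**What the plan says.** Section 6.4 handles missing outcomes and covariates by chained equations under missing at random. The number of imputations is fixed ("Ten imputation datasets will be created"), "and results pooled using Rubin's rule". The section gives no reason for ten, no expected missing rate, no check of Monte Carlo error, no rule for raising the number, and no seed.

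Section 4.3 relies on this imputation for the two co-primary estimands in the full analysis set: E1.1 (time from symptom peak to a halved ABSS) and E2.1 (antibiotic use). The per-protocol estimands E1.2 and E2.2 do not multiply impute the outcome, so the point concerns E1.1 and E2.1.

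Section 4.1 sets a 5% level for tests, "except for the co-primary outcomes, for which a 2.5% significance level is used". Section 6.2.1 says "A random seed will be predefined for replicability", but this directly follows the description of the bootstrap, and the code lines place the seed inside the bootstrap command.

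**The concern.** Multiple imputation is itself random. If the same locked database is imputed again with another seed, the pooled estimate, its standard error and its degrees of freedom all move. With few imputations the movement can carry a p-value across 0.025 when the result is close to that line.

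The ABSS endpoint looks exposed. It is built from up to 21 daily scores, and an imputed day can shift either the peak or the day on which the score is halved. Section 2.3 also makes no allowance for drop-out. At stake is whether an independent re-analysis would reach the same verdict on a co-primary outcome. A fixed seed makes one run repeatable, but a different seed, equally legitimate, could have given the other answer.

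**Working it through.** **Inputs from the SAP.** Ten imputations with Rubin pooling (6.4). Two-sided 2.5% per co-primary (4.1), critical z = 2.241. Design settings "power = 80%, a two-sided significance level = 2.5%, an allocation ratio 1:1" (2.3). ABSS: difference 1 day, SD 3 days. Antibiotics: 60% against 45%. Total 420.

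**Assumption.** The documents give no missing rate. The fraction of missing information (FMI) is therefore varied from 2% to 30%. Here it is the between-imputation share of the variance with very many imputations.

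**The plan's own figures.**
- Antibiotics, per group: (2.241 × √(2 × 0.525 × 0.475) + 0.842 × √(0.60 × 0.40 + 0.45 × 0.55))² / 0.15² = 209.4, so 210 per group and 420 in total, as stated.
- ABSS, normal formula: 2 × 3² × (2.241 + 0.842)² / 1² = 171.1, so 172 per group. The t-based version gives 172.35, so 173 per group and 346 in total, as stated.
- At 80% power the test statistic therefore centres on 2.241 + 0.842 = 3.083.

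**Step 1: seed-to-seed movement of the estimate.** In units of its standard error, the SD over seeds is √(FMI/m). At FMI 20% and m = 10 this is √(0.20/10) = 0.141. For the ABSS endpoint the design standard error is 3 × √(2/210) = 0.293 days, so the movement is 0.141 × 0.293 = 0.041 days.

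**Step 2: a result whose stable p-value is exactly 0.025, FMI 20%.** With the standard error held fixed:
- m = 10: z = 2.241 ± 1.96 × 0.141, or 1.965 to 2.517, so p from about 0.012 to 0.049.
- m = 100: SD = √(0.20/100) = 0.045, so z = 2.241 ± 0.088 and p from about 0.020 to 0.031.

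This understates the spread, because the between-imputation variance is also estimated from only m draws. Drawing it as a scaled chi-square on m − 1 degrees of freedom, and using a t reference with Barnard-Rubin degrees of freedom (complete-data 418), gives 95% ranges over seeds of about 0.011–0.065 (m = 10) and 0.020–0.034 (m = 100). At m = 10 the range is about 0.020–0.032 for FMI 2%, 0.015–0.046 for 10% and 0.008–0.084 for 30%.

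**Step 3: how often this matters.** The many-imputation statistic is drawn from a normal distribution with mean 3.083 and SD 1. Each simulated trial is then imputed twice independently, as in step 2, and the verdicts at 0.025 are compared.

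| FMI (assumed) | SD over seeds, m = 10 | Two runs disagree, m = 10 | Two runs disagree, m = 100 |
|---|---|---|---|
| 2% | 0.045 | 1.5% | 0.5% |
| 5% | 0.071 | 2.5% | 0.8% |
| 10% | 0.100 | 4% | 1.1% |
| 20% | 0.141 | 6% | 1.8% |
| 30% | 0.173 | 9% | 2.4% |

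Moving from 10 to 100 imputations also recovers roughly 0.5 to 2.5 points of power over FMI 10% to 30%.

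**Step 4: variant.** If missing data also weaken the test (mean 3.083 × √(1 − FMI), since nothing was added for drop-out), disagreement at m = 10 is 2.6%, 4.3%, 7.6% and 11.1% for FMI 5%, 10%, 20% and 30%. At m = 100 it is 0.8%, 1.3%, 2.2% and 3.2%.

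**The case against.** The strongest reply is that nothing here is invalid. Rubin's variance already contains the between-imputation variance divided by m, so the reported interval and p-value allow for a finite number of imputations. The seed noise adds in quadrature: 0.100², 0.141² and 0.173² are about 1%, 2% and 3% of the variance at FMI 10%, 20% and 30%. That stands. A reader might infer from the ranges in step 2 that the type I error is inflated or that the primary result would be unreliable. Neither follows: one prespecified run is unbiased and holds its error rate, and those ranges apply only to a result exactly at 0.025.

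Second, any finite number of imputations leaves close to a coin toss at the threshold itself. That also stands; more imputations narrow the unstable zone but do not remove it. At FMI 20% and a stable p of 0.020, two runs disagree 47% of the time with m = 10, 27% with m = 50 and 13% with m = 100.

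Third, the FMI may be low. Section 6.1 provides phone calls at days 4, 8 and 22, which ask about antibiotics and collect the ABSS when the diary was not answered. This is fair, and antibiotic use may well carry less missing information than the ABSS endpoint. The table therefore starts at 2%, where the gain is small.

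Fourth, the predefined seed, the independent code check (6.8) and possible sharing of data and code (3.4) would secure exact reproduction. They would do so only if a seed also covers the imputation, and the text does not say that it does. A reader might take the sentence in 6.2.1 to cover it, but its position and the code tie it to the bootstrap.

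**Conclusion.** The point holds as a cheap improvement in precision and reproducibility, not as a flaw in validity. With ten imputations, two equally sound runs would reach opposite verdicts on a co-primary in about 1.5% to 9% of trials over FMI 2% to 30%. With 100 imputations this falls to about 0.5% to 2.4%. The separate gap is plain from the text: no seed is stated for the imputation.

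The size rests on the assumed FMI, on an effect with 80% power, and on taking the imputation model as correct. For the ABSS endpoint, 420 participants exceed the 346 required, so at its design effect disagreement would be somewhat lower than tabulated. The bootstrap adds smaller noise of its own, which is not in the table: 1000 replications give a standard error with a coefficient of variation of about 1/√2000 = 2.2%.

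**What to change.** In section 6.4, before database lock:
- replace ten by 100 imputations for E1.1 and E2.1;
- predefine a seed for the imputation as well as for the bootstrap;
- commit to reporting the Monte Carlo error of each co-primary estimate and p-value.

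The cost is computing time: 100 chained-equation runs over the daily scores instead of ten and, if the bootstrap is run within each imputed data set, 100 × 1000 = 100,000 regression fits per model instead of 10 × 1000 = 10,000. The SAP does not state the order of bootstrap and imputation. If imputation is repeated inside each bootstrap sample, the load is heavier, because the chained equations are then run 100,000 times instead of 10,000. Trial conduct, participants and sample size are not affected.

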4.3 Estimands

We define the following estimands for the outcomes.

Estimand E1.1: This estimand quantifies the effectiveness of the treatment assessed with the reduction of symptom severity (co-primary outcome).

Outcome of interest: Number of days needed to achieve a 50% reduction on the Acute Bronchitis Severity Score (ABSS) after peak of symptoms, assessed at max. 22 days. The peak of symptoms is defined by the highest ABSS (or the initial score if there is no peak). This is a normally distributed count outcome (3).

Population-level summary measure of outcome: adjusted* mean difference.

Participant-set of interest: FAS.

Handling of intercurrent events: All participants are included.

Handling of missing data: Missing data will be multiple imputed (see section 6.4).

* 1) Adjusted for the type of recruitment (PCP/walk-in clinic) and 2) adjusted for the following factors at baseline: type of recruitment, age, sex, level of education, smoking status, beginning of symptoms (number of days), baseline ABSS, and prescriptions for corticosteroid containing oral medication or inhalers (yes/no), including Prednisone, Symbicort, and Vannair.

Estimand E1.2: This estimand quantifies the effectiveness of the treatment assessed with the reduction of symptom severity (co-primary outcome) in the PP population.

Outcome of interest: Same as estimand 1.1.

Population-level summary measure of outcome: same as estimand 1.1.

Participant-set of interest: PP.

Handling of intercurrent events: Participants with ICE1-3 are excluded from the analysis. The data will be weighted according to inverse probability weighting for ICE 1 and 2 (see section 6.2.2).

Handling of missing data: As ICE cannot be assessed in participants who drop out or are lost to follow-up, we will not use multiple imputation. We will use inverse probability of attrition weights to account for attrition and multiple imputation for missing baseline covariates (see section 6.4).

SAP for PHYTOBRONCH	Version of SAP: 1	
Based on template: CTU_STA_TEM-11; v5.0.0	Valid from: 20.03.2025	Page 8 of 15

Estimand E2.1: This estimand quantifies the efficacy of the treatment assessed with the proportion of antibiotics use (co-primary outcome).

Outcome of interest: Use of antibiotics after the initial visit (binary).

Population-level summary measure of outcome: adjusted* risk ratio.

Participant-set of interest: FAS.

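### The imputation model in SAP 6.4 does not name randomised group; followed literally, it pulls the antibiotics risk ratio towards 1 and, to a lesser extent, shrinks the ABSS difference

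*Combined protocol and SAP*

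**What the plan says.** For the primary analysis, section 6.2.1 states: "The randomization group will be used as the main predictor, adjusting for the stratification factors and relevant predefined covariates". It hands missing data to one place: "We will use multiple imputation to handle missing values on covariates and outcomes (see section 6.4". Section 4.3 does the same for E1.1 and E2.1.

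Section 6.4 specifies chained equations under missing at random, ten datasets and Rubin's rules. On predictors it says: "The following auxiliary variables will be used to predict missingness: type of recruitment (PCP/walk-in clinic), age, sex, level of education, smoking status", followed by days since symptom onset and baseline ABSS. Any listed variable that itself has missing values is dropped from the list. Terminal events and technical causes of missingness are added. Randomised group does not appear, and no other section says that imputation uses group or is run by arm.

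The fully adjusted E1.1 model also contains "prescriptions for corticosteroid containing oral medication or inhalers (yes/no"; E2.1 takes the "Same adjustment as E1.1". That covariate is not in the 6.4 list either.

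For the ABSS endpoint, section 6.1 says: "Imputation will be used for missing values on daily ABSS". The endpoint is then derived from the daily scores. A sensitivity analysis imputes the derived endpoint directly.

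**The concern.** An imputation model should contain every variable whose effect the analysis model estimates. If group is left out, imputed outcomes carry no treatment effect beyond what other observed variables happen to transmit. The completed data then mix real outcomes, which show the effect, with imputed ones that do not. Group is fully observed, so chained equations do not bring it in automatically as they do an incomplete variable; it has to be specified.

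What is at stake is an attenuated co-primary estimate and lost power, beyond the loss that missing data cause anyway. The subgroup analyses in 6.2.4 would inherit the problem if they use the same imputed datasets. Because the trial is open-label, the predictor list is better fixed now than chosen once the data are available.

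**Working it through.** **Inputs (section 2.3).** Antibiotic use 60% (control) and 45% (intervention), so RR = 0.45/0.60 = 0.75. ABSS difference 1 day, SD 3. Two-sided alpha 0.025 per outcome, power 80%, 1:1, n=420, no drop-out allowance. The missing-outcome share *m* is not given; 5, 10 and 20% are assumed.

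**The plan's own figures.** Pooled-variance test of two proportions, with pooled rate 0.525:

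n per arm = [2.2414·√(2·0.525·0.475) + 0.8416·√(0.60·0.40 + 0.45·0.55)]² / 0.15² = 209.4, rounded up to 210, or 420 in total, as stated. Power at 210 per arm is 80.1%. For the means, the normal formula gives 172 per arm against the stated 173, which is close enough.

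**Antibiotics, group omitted.** With equal missingness in both arms and no other informative predictor, missing outcomes in both arms are drawn at the pooled rate 0.525:

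RR(m) = [(1−m)·0.45 + m·0.525] / [(1−m)·0.60 + m·0.525]

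- 5%: 0.45375/0.59625 = 0.761
- 10%: 0.4575/0.5925 = 0.772
- 20%: 0.465/0.585 = 0.795

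Power was simulated with n=420, ten proper imputations, Rubin's rules, a Wald test on log RR at alpha 0.025, completely random missingness, no clustering and 10,000 trials per setting. Complete-data power for this test is about 79%.

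| Missing | RR, group omitted | Power without group | Power with group |
|---|---|---|---|
| 5% | 0.761 | 74% | 77% |
| 10% | 0.772 | 66% | 73% |
| 20% | 0.795 | 48% | 67% |

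At 20%, the fall from about 80% to 67% is due to missing data itself; only the further fall to 48% is due to omitting group. Larger repeat runs agreed within about two points. One run of only 2,000 trials gave narrower gaps at 5% (73 vs 74%) and 10% (68 vs 72%). With group included, the simulated RR stayed at about 0.75. With no true effect and 20% missing, the group-omitted analysis rejected in about 0.5% of trials, against 2.5% nominal.

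If ABSS is observed in these participants and predicts antibiotic use (assumed within-arm correlation 0.2, 0.3 or 0.5), RR at 20% missing is about 0.78, 0.78 or 0.77. The range at 20% is therefore 0.77 to 0.795.

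**ABSS, derived endpoint imputed (sensitivity analysis).** The difference kept is (1−m)·1 day: 0.95, 0.90 and 0.80. Power without vs with group is 83 vs 85%, 76 vs 83% and 60 vs 77% (6,000 trials per setting).

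**ABSS, daily scores imputed (primary analysis).** Earlier days predict later ones and carry most of the group difference. Illustrative decaying symptom curves were used, with 20% drop-out, all earlier days in the chain, group omitted and 1,500 trials per setting:

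| What is observed in drop-outs | Share of true difference kept |
|---|---|
| Diary to day 8 | 100% |
| Diary to day 4 | 99% |
| Last day spread over days 1–8 | 96% (power 74 vs 77% with group) |
| Day 4, 8 and 22 phone scores | about 100% |
| Nothing after day 1 | 80% |

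With only the two preceding days as predictors, 93% (day 4) and 98% (day 8) were kept. A separate simulation with different curves gave 98% (day 8), 95% (day 4), 84% (day 2) and 81% (day 1). With noisier daily scores, a linear-normal imputation that included group overshot in some settings (115% when nothing followed day 1), because the endpoint is a threshold crossing. The curves are assumed, so these figures show relative size only.

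**The case against.** The strongest reply concerns the word *auxiliary*. In multiple imputation it usually means variables added to those of the analysis model, and 6.2.1 makes group the main predictor of that model. Section 6.4 neither calls the list exhaustive nor excludes group, so the intention may well be standard practice.

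That reading is possible, but the text does not support it well. All seven listed baseline variables are already E1.1/E2.1 covariates, so they are not extras; they are exactly the E3.1 set ("type of recruitment, age, sex, level of education, smoking status, beginning of symptoms (number of days), and baseline ABSS"). Dropping incomplete variables from the list would have little purpose if they were in the model anyway. An independent code check (section 6.8) would have nothing on this point to check against.

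The points on size largely stand:

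- The missing rate is unknown. At 2% missing, RR is 0.754 and power 77 vs 79%.
- Follow-up is short and has a backup: "If the participant does not answer, the ABSS will be evaluated in phone interviews (days 4, 8, and 22"; antibiotic use is also asked at those calls. Anyone who reports use after the initial visit before being lost is already a known event. In one illustration (20% lost, last contact spread over days 1–8, mean delay to antibiotics about 4 days), only 14–15% have unknown status.
- The 48% power figure is therefore an upper scenario.
- The primary ABSS analysis is hardly affected unless drop-outs give nothing after day 1.
- The missing corticosteroid covariate is a mismatch with the analysis model; it was not shown to bias the effect.

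**Conclusion.** The concern holds and should be fixed. Section 6.4 gives an explicit predictor list without randomised group, and applying it literally biases the antibiotics estimate towards no difference: from RR 0.75 to between 0.761 and 0.795 over assumed missing rates of 5 to 20%, with 3 to 19 points of power lost beyond what missing data cost anyway. The same mechanism acts on the ABSS sensitivity analysis that imputes the derived endpoint. The primary ABSS analysis is affected much less.

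The direction is conservative and does not raise false positives. The per-protocol estimands do not impute outcomes, so they are untouched by this route. The power figures assume completely random missingness, no clustering and no covariates. Confidence is medium, because the sponsor may have meant group to be included and because the missing rate is not stated.

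**What to change.** In section 6.4, state that imputation is run separately by randomised group, or that group enters every imputation equation. State also that all analysis-model covariates, including corticosteroid prescription, and the other daily ABSS scores are in the imputation model. The same rule should cover the sensitivity analysis that imputes the derived endpoint.

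The cost is a few sentences and the imputation code; no new data are needed. The practical downside is slightly more coding and possible convergence trouble with up to 21 correlated daily scores in arms of about 210. If group was always intended, the edit changes no analysis and removes the ambiguity.
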